9.4.4 SAFETY ANALYSES

Total adverse events and total serious adverse events will be reported to the Data Safety Monitoring Committee (DSMC), tabulated by surgery and drug. Serious adverse event reporting to the DSMC and the medical monitor will be conducted within 24 hours. Individual adverse events will be tabulated by treatment allocation and included in DSMC reports, on a schedule to be determined by the empaneled DSMC prior to enrollment.

9.4.5 BASELINE DESCRIPTIVE STATISTICS

Baseline statistics will be similar to those in DETECT-TES, which you can see below.³¹ We will be looking at comparable baseline demographic characteristics, including age and sex; clinical characteristics, including diagnosis, BSCVA, central corneal thickness, manifest refraction, concurrent cataract surgery; and donor characteristics including age, sex, death to preservation time, death to surgery time, endothelial cell count pre- and post-processing, and central graft thickness in UT-DSAEK grafts.

Table 1. Baseline Characteristics

	UT-DSAEK (N=25)	DMEK (N=25)	P*
Patient characteristics			
Age (yrs), mean (range)	68 (51–95)	68 (61–81)	0.96
Female sex, N (%)	16 (64%)	13 (52%)	0.39
Diagnosis, N (%)			
Fuchs	24 (96%)	24 (96%)	1.00
PBK	1 (4%)	1 (4%)	
ETDRS BSCVA, mean ± SD			
logMAR	0.27±0.21	0.34±0.29	0.34
Approximate Snellen	20/40	20/40	
CCT (µm), mean ± SD	610±44 [†]	608±52	0.93
Spherical equivalent (diopters), mean ± SD	−0.4±1.9	−0.8±2.2	0.53
Surgery, N (%)			
Pseudophakic EK	8 (32%)	7 (28%)	0.76
Triple EK	17 (68%)	18 (72%)	
Donor characteristics			
Age (yrs), mean (range)	64 (54–75)	62 (50–76)	0.38
Female sex, N (%)	8 (32%)	5 (20%)	0.33
Death to preservation (hrs), mean ± SD	9±4	9±3	0.80
Death to surgery (days), hrs ± SD	6±1	6±1	0.61
ECC preprocessing (cells/mm ²), mean ± SD	2792±210	2797±222	0.94
ECC postprocessing (cells/mm ²), mean ± SD	2796±238	2771±150	0.66
Central graft thickness, mean ± SD (range)	73±12 (37–88)	—	—

BSCVA = best spectacle-corrected visual acuity; CCT = central corneal thickness; DMEK = Descemet membrane endothelial keratoplasty; ECC = endothelial cell count; EK = endothelial keratoplasty; ETDRS = Early Treatment Diabetic Retinopathy Study; logMAR = logarithm of the minimum angle of resolution; PBK = pseudophakic bullous keratopathy; SD = standard deviation; UT-DSAEK = ultrathin Descemet stripping automated endothelial keratoplasty.

*t tests for continuous variables and chi-square tests for categorical variables.

[†]One missing value.

9.4.6 PLANNED INTERIM ANALYSES

A Data and Safety Monitoring Committee (DSMC) has been empaneled by the NEI. This committee consists of 5 individuals, and includes (a) cornea specialists, (b) an independent biostatistician, and (c) a bioethicist. The committee will meet in person at least once per year and will convene biannual teleconferences for progress reports. *Ad hoc*

DETECT

Version 5.0
21 March 2023

meetings as needed may also be convened. All study protocols will be subject to review and approval by Institutional Review Boards.

The Data and Safety Monitoring Committee will meet to review the interim efficacy data for each trial when primary outcome data is available on one third of the study subjects. The DSMC will make one of the following recommendations:

- Continue the trial without modifications
- Continue the trial with study modifications
- Terminate enrollment or treatment in the trial because of safety concerns
- Terminate enrollment or treatment in the trial because of efficacy
- Terminate enrollment or treatment in the trial because of futility

Interim reports for the DSMC will be prepared by the Data Coordinating Center. These reports will include (a) recruitment overall, and by study site, (b) compliance, and (c) retention. The reports will also list study outcomes, and all adverse outcomes, including medication side effects, primary graft failure, graft rejection, and mortality. The DSMC will determine the database closure dates for each report in advance; archival copies of the (a) main database, and (b) study analysis files as they exist at the time of each report will be maintained. All reports will be sent using secure email to the members of the DSMC two weeks prior to each meeting.

The DSMC will make decisions with the benefit of pre-specified decision guidelines. These guidelines will be agreed upon at the initial meeting, and are expected to include (a) safety, (b) efficacy, (c) clinical importance, (d) effect of baseline covariates, or (e) validity.

We propose the same interim analysis approach for both DETECT I and DETECT II trials.

Benefits. An unmasked interim analysis will be conducted to determine whether or not sufficient evidence has accumulated to justify stopping one or both factorial treatments. The guidelines for efficacy will use group sequential boundaries for judging the statistical significance of the primary outcome measure. The trial will use the Lan and DeMets flexible alpha spending approach with a power function, with $\alpha^*(t^*) = \alpha (t^*)^\theta$, where $\alpha = 3.561$ (chosen so that the two-sided P -value to stop the trial for efficacy is 0.001).⁵⁴ We propose a single interim analysis at the midpoint of the trial, i.e. when full outcome data are available for one half of the subjects. If one surgery method is clearly superior with respect to BSCVA, with no evidence for interaction with the ripasudil, then future patients will receive the better surgery method and still be randomized to ripasudil vs placebo. If ripasudil is clearly superior to placebo with respect to ECD, with no evidence for interaction by type of surgery, then future patients will receive ripasudil and would still be randomized to surgery type. At the interim analysis, tests for interaction will have very low power and so any decision to stop a single treatment early for benefit would be done in consultation with the DSMC.

Harm. Stopping one or both treatments for harm will be done at the judgment of the DSMC. Several endpoints will be examined, including (a) the best spectacle-corrected visual acuity at 12 months (b) adverse events, and especially (c) serious adverse events, including primary graft failure or mortality. While the analysis would consider maldistribution of predictive factors such as (a) age (b) visual acuity at presentation, and (c) diagnosis of PACE, it is recognized that ethical considerations require careful considerations of statistical tests as well as qualitative judgments in the light of experience.

Futility. Early discontinuation due to the unlikelihood of significant findings for both primary analyses conditional on interim results may be considered pending discussion with the DSMC.

DETECT

Version 5.0
21 March 2023

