All study participants will be masked to their intervention. The refractionist performing the BSCVA will also be masked. Due to the nature of the intervention, the surgeon and technician performing study visit endothelial cell density and other imaging will not be masked as to surgery type (but will be masked as to study medication); however, the image graders at the Proctor Reading Center and CIARC will be masked. All study medications and placebo will be labelled identically to ensure adequate masking of study physicians and patients. An interim analysis will be performed once primary outcome data is available for one half of the patients (see **Section 9.4.6** of this protocol for details). The enrollment period is 24 months.

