9.2 SAMPLE SIZE DETERMINATION

DETECT I

We will power the study for each comparison. For both primary analyses, we used a standard sample size formula based on an ANCOVA that conditions on a baseline outcome measure.⁴⁹ Given that endothelial cell density and visual acuity are different, non-correlated outcomes ($R=0.08$ in the DETECT pilot study) with different randomization, each will have its own alpha of 0.05. Specifically, we will be comparing:

- I. With 80 patients per group (160 total), we estimate that we will have at least 90% power to detect a difference in logMAR of 0.11 at 12 months, assuming an outcome SD of 0.2, a 2-sided alpha of 0.05, and 10% loss-to-follow-up. Under the same assumptions but 80% power, the minimum detectable difference in logMAR is 0.09. We assumed a higher SD in the calculation compared with the SD estimated in the DETECT pilot (adj. SD=0.147) to allow for more complex eyes enrolled in the trial.
- II. With 80 patients per group (160 total), we estimate that we will have at least 90% power to detect a 7% difference in ECL between enrollment and 12 months, assuming an outcome SD of 0.134 estimated from the DETECT pilot study, a 2-sided alpha of 0.05, and 10% loss-to-follow-up. If we assume a larger outcome SD for more complex eyes (SD=0.18), we will have at least 90% power to detect a 10% difference in ECL.

DETECT II

With 30 patients per group (60 total), we estimate that we will have at least 90% power to detect a difference in logMAR of 0.13, assuming an outcome SD of 0.147, a 2-sided alpha of 0.05, and 10% loss-to-follow-up. The SD was estimated from the DETECT pilot study and was adjusted for correlation between baseline and 12-month measurements (outcome SD = 0.163, correlation = 0.428, adjusted SD = 0.147). Under the same assumptions but 80% power, the minimum detectable difference is 0.11 logMAR.

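### The interim efficacy rule contradicts itself: exponent 3.561 gives the stated stopping P of 0.001 only at one third of the data, but the look is set at one half, where it gives 0.0042

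*Protocol*

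**What the plan says.** Section 9.4.6 of the protocol describes the interim efficacy look twice, and section 4.1 describes it once.

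- The general part of 9.4.6 has the data and safety monitoring committee (DSMC) review interim efficacy data for each trial "when primary outcome data is available on one third of the study subjects". Stopping for efficacy is among the recommendations it may make.
- The Benefits paragraph of 9.4.6 says: "We propose a single interim analysis at the midpoint of the trial, i.e. when full outcome data are available for one half".
- Section 4.1 agrees with the Benefits paragraph: "An interim analysis will be performed once primary outcome data is available for one half of the patients".

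The Benefits paragraph also fixes the boundary: "The trial will use the Lan and DeMets flexible alpha spending approach with a power function". The cumulative alpha at information fraction t is alpha × t^theta. The parameter is given as 3.561, and the reason given for that value is that the two-sided P-value "to stop the trial for efficacy is 0.001".

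The alpha to be spent comes from section 9.2. For the two DETECT I primary outcomes, "each will have its own alpha of 0.05", and the tests are two-sided. DETECT II is also sized at two-sided 0.05. Section 9.4.6 applies the same interim approach to both trials.

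**The concern.** At the first and only interim look, the nominal P-value boundary equals the alpha spent up to that look. Once the look time and the exponent are fixed, the stopping P-value follows and cannot be chosen separately. The protocol fixes all three, and it gives two values for the look time.

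This boundary is the efficacy guideline for deciding whether later DETECT I patients are still randomized between surgeries, or between ripasudil and placebo. It is also the efficacy guideline for DETECT II. A statistician who programs the stated function at the midpoint and one who applies the stated P-value would use different thresholds, and each could cite the protocol. The analysis is unmasked, so the choice between them should not still be open when the data are seen.

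**Working it through.** **Inputs**

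- Alpha = 0.05, two-sided, for each primary comparison (section 9.2).
- Spending function alpha × t^theta, parameter 3.561, target two-sided P = 0.001 (9.4.6, Benefits). I read 3.561 as theta: it cannot be a significance level, and step 1 confirms the reading.
- Look time t = 1/2 (4.1; 9.4.6, Benefits) or t = 1/3 (9.4.6, general part). Information is taken as proportional to subjects with outcome data.
- SD 0.2 logMAR and 80 patients per group in DETECT I; SD 0.147 and 30 per group in DETECT II; 10% loss in both (section 9.2).

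**Step 1. Reproduce the stated 0.001**

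| Look time t | 0.05 × t^3.561 | Boundary on \|z\| |
|---|---|---|
| 1/3 | 0.00100 | 3.29 |
| 1/2 | 0.00424 | 2.86 |

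The stated value is reproduced at one third and not at one half. Spending 0.025 on each side does not help: 0.025 × (1/2)^3.561 = 0.00212 per side, which is again 0.00424 two-sided.

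**Step 2. Solve for the exponent**

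Setting 0.05 × t^theta = 0.001 gives theta = ln(50) / ln(1/t).

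- t = 1/3: theta = 3.912 / 1.0986 = 3.561.
- t = 1/2: theta = 3.912 / 0.6931 = 5.644.

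The agreement to three decimals at one third shows which look time the printed exponent was derived for.

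**Step 3. What the two readings mean at a midpoint look**

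The smallest observed difference that crosses is z × SD × sqrt(2/n), where n is the number evaluable per group. Taking half of enrollment less 10% loss gives n = 40 × 0.9 = 36 in DETECT I and n = 15 × 0.9 = 13.5 in DETECT II. The standard errors are 0.2 × sqrt(2/36) = 0.0471 and 0.147 × sqrt(2/13.5) = 0.0566.

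| | Function followed (P = 0.0042) | Stated P followed (0.001) |
|---|---|---|
| DETECT I boundary | 2.860 × 0.0471 = 0.135 logMAR | 3.291 × 0.0471 = 0.155 logMAR |
| DETECT II boundary | 2.860 × 0.0566 = 0.162 logMAR | 3.291 × 0.0566 = 0.186 logMAR |

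For the chance of crossing in DETECT I, assume a true difference of 0.14 logMAR. This is the pilot's 1.4 lines at 12 months, at 0.1 logMAR per line. The expected z is 0.14 / 0.0471 = 2.97. The chance of crossing in the favourable direction is P(Z > 2.860 − 2.970) = 54% under the function and P(Z > 3.291 − 2.970) = 37% under the stated P.

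**Step 4. Final analysis**

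The final critical value makes the total two-sided error 0.05, using the bivariate normal distribution with correlation sqrt(t).

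| Look | Exponent | Interim P | Final nominal two-sided level |
|---|---|---|---|
| 1/2 | 3.561 | 0.0042 | 0.0485 |
| 1/2 | 5.644 | 0.0010 | 0.0498 |
| 1/3 | 3.561 | 0.0010 | 0.0495 |

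**The case against.** The arithmetic is hard to dispute. The case on the other side concerns how much it matters.

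- **The target is explicit.** The exponent is said to be chosen to give P = 0.001, so a careful reader would keep 0.001 and re-derive the exponent. That is a reasonable guess at the intention. It still departs from the stated function, and it does not settle whether the look is at one third or one half.
- **Type I error is not at risk.** This stands. Lan-DeMets spending holds the overall level at 0.05 for either look time if the final boundary is computed from the alpha actually spent. The final levels in the working differ by only about 0.001.
- **The rule is a guideline.** Section 9.4.6 leaves decisions to stop a single treatment for benefit to consultation with the DSMC. That softens the consequence. The committee is nevertheless meant to work from prespecified guidelines, and this is the only numerical efficacy guideline in the protocol.
- **Few patients may be affected.** Enrollment lasts 24 months and the endpoint is at 12 months. With uniform accrual (an assumption), half the subjects have 12-month data at about month 24, when enrollment is ending. This stands as a limit on the practical effect of a midpoint look.
- **The logMAR boundaries depend on choices.** If one half means 40 patients per group with data, the DETECT I boundaries are 0.128 and 0.147 logMAR and the crossing chances 61% and 44%. With t quantiles (24 degrees of freedom), the DETECT II boundaries are about 0.179 and 0.212. The pilot effect behind the crossing chances was itself imprecise. The gap between the two readings remains in each case.
- **The symbol.** The text available to me prints alpha, not theta, in front of 3.561. This may come from reading the PDF, and nothing here depends on it.

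**Conclusion.** The inconsistency is real and lies in the current protocol text. A single midpoint look, exponent 3.561 and a stopping P of 0.001 cannot all hold. The last two fit together only at one third, which is the look time given elsewhere in the same section.

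At the midpoint the two readings differ by a factor of 4.2 in P (0.0042 against 0.001). In DETECT I, an observed acuity difference between 0.135 and 0.155 logMAR would cross under one reading and not the other.

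The P-values and exponents rest only on alpha = 0.05 and on information being proportional to subjects with data. The logMAR boundaries also assume the section 9.2 SDs, 10% loss and normal quantiles, and the crossing chances further assume a true difference of 0.14 logMAR. The overall false-positive rate is not inflated, provided the final boundary is computed from the alpha spent. The point must be corrected because it leaves the efficacy stopping threshold undefined in both trials.

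**What to change.** - State one look time in section 4.1 and in both parts of section 9.4.6.
- Match the exponent to it: theta = 3.561 for one third, or theta = 5.644 for one half. Either gives an interim two-sided P of 0.001.
- If the source document does print alpha in front of 3.561, change it to theta.
- State that the information fraction actually reached at the look is entered in the spending function, so that the interim boundary moves with it. Give the planned final nominal level: about 0.0495 for a one-third look or 0.0498 for a one-half look.

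This changes protocol wording only. It needs no more patients and no additional analysis. It should be settled before any unmasked interim data are reviewed.

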9 STATISTICAL CONSIDERATIONS

9.1 STATISTICAL HYPOTHESES

Specific Aim 1: To determine whether DMEK has superior post-operative best spectacle corrected visual acuity (BSCVA) compared with UT-DSAEK or DSO with a similar safety profile.

- We hypothesize that the DMEK group will have improved visual acuity compared with UT-DSAEK at all time points.*
- We hypothesize that the DMEK group will have improved visual acuity compared with DSO at all time points.*

Specific Aim 2: To determine the benefit of adjuvant rho-kinase inhibitors on endothelial cell loss in patients who received UT-DSAEK and DMEK.

- We hypothesize that endothelial cell loss will be higher after DMEK than UT-DSAEK.*
- We hypothesize that endothelial cell loss will be lessened among those receiving ripasudil, after controlling for the pre-operative ECD in DMEK and UT-DSAEK.*

Primary Endpoints:

- Best spectacle-corrected visual acuity (BSCVA) at 12 months
- Endothelial cell loss at 12 months

Secondary Endpoints:

- Specific Aim 1: BSCVA at 3, 6, and 24 months
- Specific Aim 1: Complications over the course of the entire study period, including re-bubble rate, graft rejection, primary graft failure, and need for further surgery.
- Specific Aim 2: Endothelial cell density at 3, 6, and 24 months
- National Eye Institute Visual Function Questionnaire (VFQ) post-operatively at 3 months and 12 months as compared to baseline
- Adverse events over entire study period
- Corneal haze and higher-order aberrations as measured by Pentacam at baseline and post-operatively at 3, 6, 12, 24 months
- Graft thickness as measured by optical coherence tomography and pachymetry on donor tissue pre-operatively and post-operatively at 6 and 12 months
- Cost-effectiveness analysis at 24 months
- Manifest refraction at baseline and post-operatively at 3, 6, 12, 24 months

DETECT

Version 5.0
21 March 2023

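### At the one-half trigger the efficacy look falls at about the end of the 24-month enrolment, so the reallocation rule for future patients would reach few or none; the interim fraction, the spending exponent and the enrolment timeline need reconciling

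*Protocol*

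**What the plan says.** On timing, section 4.1 gives the accrual plan, "The enrollment period is 24 months", and the trigger, "An interim analysis will be performed once primary outcome data is available for one half of the patients". The Benefits paragraph of section 9.4.6 repeats the midpoint: a single look "when full outcome data are available for one half of the subjects". Earlier in section 9.4.6, however, the DSMC is to review interim efficacy data "when primary outcome data is available on one third of the study subjects".

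The DETECT I primary endpoints in section 9.1 are "Best spectacle-corrected visual acuity (BSCVA) at 12 months" and endothelial cell loss, also at 12 months. DETECT II uses 12-month BSCVA.

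Section 9.4.6 names an action for each factor. If a surgery wins, "then future patients will receive the better surgery method and still be randomized to ripasudil vs placebo". If ripasudil wins, "then future patients will receive ripasudil and would still be randomized to surgery type". The same interim approach is proposed for DETECT I and DETECT II. The boundary is a power-family spending function with exponent 3.561, said to be chosen to give a two-sided P of 0.001 for stopping.

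**The concern.** The reallocation rule can help only patients who have not yet been randomized when the DSMC acts. A 12-month endpoint read on half the sample, within a 24-month accrual period, leaves almost no time between the look and the last enrolment. If nobody is left, the DSMC holds a pre-specified decision rule that it cannot carry out. Surgery is done once and the drops run for three months, so reallocation could do little for patients already randomized.

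The protocol itself fixes the trigger, the enrolment period, the endpoint time and the action. It also gives two different trigger fractions, and the boundary matches the one that does not appear in the Benefits paragraph.

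**Working it through.** **Inputs.** Enrolment 24 months (synopsis and 4.1); endpoint at 12 months (9.1); visit window 10 to 14 months (5.5); trigger one half (4.1, and Benefits in 9.4.6) or one third (9.4.6, DSMC review); N = 160 and 60; SD 0.2, 10% loss and two-sided alpha 0.05 (9.2). The protocol gives no accrual curve, so even accrual is an assumption, varied below.

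**The plan's own figures first.** With 80 × 0.9 = 72 per arm, SD 0.2 and a difference of 0.11 logMAR, power is 0.910, in line with the stated 90%. At a first look, the P-value boundary equals the alpha spent, 0.05 × t^3.561:

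- t = 1/3: 0.0010, the stated value.
- t = 1/2: 0.0042, about four times the stated value.
- Exponent needed for 0.001 at one half: ln(50)/ln(2) = 5.644. At one third: ln(50)/ln(3) = 3.561.

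The exponent is therefore the one that belongs to a one-third look.

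**Month of the look.** T = 24 × f/(1 − loss) + visit month + processing time. Patients still to enrol = N × max(0, 1 − T/24).

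| Trigger and case (even accrual) | T (months) | Left of 160 |
|---|---|---|
| One half, no loss, visits at 12 | 24.0 | 0 |
| One half, 10% loss, visits at 12 | 25.3 | 0 |
| One half, no loss, visits at 14 | 26.0 | 0 |
| One half, no loss, visits at 10 | 22.0 | 13 (8%) |
| Same, one month of processing | 23.0 | 7 (4%) |
| One half, 10% loss, visits at 10 | 23.3 | 4 (3%) |
| One third, no loss, visits at 12 | 20.0 | 27 (17%) |
| Same, one month of processing | 21.0 | 20 (12%) |

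For DETECT II, with no loss and visits at 12 months, one half gives month 24 and 0 of 60 left; one third gives month 20 and 10 of 60 left.

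**Uneven accrual.** Let the enrolled fraction be (t/24)^g, with visits at 12 months and no loss. At one half:

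- Slow start, g = 1.25 to 2: months 25.8 to 29.0, 0 left.
- Front-loaded, g = 0.8 to 0.7: months 22.1 to 20.9, 10 to 15 of 160 left (6 to 9%), or 5 to 10 after one month of processing.

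The 9% ceiling takes one favourable departure at a time. Combining g = 0.7 with every visit at 10 months gives T = 24 × 0.5^(1/0.7) + 10 = 18.9, and 160 × (1 − (18.9/24)^0.7) ≈ 25 left (15%). That combination needs all patients at the early edge of the window, no loss and no processing time.

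**Chance of crossing P = 0.001.** Take a true difference of 0.14 logMAR (the 1.4 lines at 12 months reported for the earlier trial in section 2.1, at 0.1 logMAR per line) and SD 0.2. The noncentrality is 0.14/(0.2 × √(2/n)) and the critical value is 3.29.

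| Look | n per arm | Chance |
|---|---|---|
| One third, no loss | 26.7 | 23% |
| One third, 10% loss | 24 | 19% |
| One half, no loss | 40 | 44% |
| One half, 10% loss | 36 | 37% |

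**The case against.** The strongest reply is that the look does more than reallocate. Section 9.4.6 also lets the DSMC recommend study modifications, or terminating enrolment or treatment for efficacy, safety or futility, and it describes harm and futility reviews. A reader might infer that reallocation is the only efficacy action, or that the look cannot benefit anyone. The text supports neither. At month 24 under even accrual, about 160 × 3/24 = 20 patients would still be within the three-month drop course, so a recommendation about treatment would still reach people. Only the two sentences about future patients are affected.

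Two other tempting arguments fail. The gap of weeks to months between enrolment and surgery (5.4) does not make matters worse: a common delay moves the look and the last randomization together. It does not rescue the rule either. The visit window is symmetric, so it can bring the look forward as well as push it back.

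Nor is alpha cost an argument. One look at P = 0.001 at one half leaves a final two-sided level of about 0.0498; at 0.0042 it leaves about 0.0485.

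It is also fair to say that zero is not certain. No accrual curve is given, and enrolment can overrun. If the same sample took 30 or 36 months, the half-way look would fall at month 27 or 30, leaving 160 × (1 − 27/30) = 16 or 160 × (1 − 30/36) ≈ 27 patients. That would rest on missing the stated timeline.

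Finally, the protocol does not settle on one half. This is right, and it makes the mismatch of fractions part of the same point.

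**Conclusion.** The point holds in a limited form. Under the stated 24-month enrolment and roughly even accrual, the one-half look comes at about month 24 or later, and the reallocation rule would reach 0 of 160 and 0 of 60 patients. Front-loaded accrual alone, or visits all at 10 months alone, leaves at most about 9% of 160. Loss to follow-up, a slow start and reporting time all push the look later.

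The one-third statement in section 9.4.6 and the exponent of 3.561 agree with each other and disagree with the midpoint in 4.1 and in the Benefits paragraph. The final analysis is not invalidated. The defect is a decision rule that probably cannot operate as written, alongside a trigger and a boundary that do not match. It should be corrected.

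**What to change.** Reconcile the interim fraction, the exponent and the enrolment timeline in sections 4.1 and 9.4.6.

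- **Simplest route: state one third throughout.** This keeps 3.561 and P = 0.001. The text should say that the look is expected at about month 20, with about 27 of 160 and 10 of 60 patients still to enrol under even accrual, and fewer after image reading, report preparation and the two-week DSMC mailing. The cost is wording plus a lower chance of crossing: about 19 to 23% against 37 to 44% at one half, for a true 0.14 logMAR difference with P = 0.001 at both looks.
- **If one half is kept:** change the exponent to about 5.64 so that it yields 0.001. Delete the reallocation sentences, or restate them to say that they are expected to affect few or no patients. Keep the harm and futility reviews.

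Either way, the protocol should state the accrual pattern it assumes, so that the calendar month of the look can be checked.
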